5.9 Data Collection and multi-center procedure

Data will be collected on uniform CRFs provided by MDACC. These are to be completed for baseline information and throughout the study as required by the protocol and faxed within 4 weeks after completion of each cycle to:

[name]

Ph:[contact]

[contact]

After patients have completed therapy, completed CRFs will be faxed within 1 month of patient's follow-up visit.

5.10

MDACC's data monitoring committee will review the study. Quarterly conference calls among Principal Investigators and support staff will take place to review enrollment and any safety issues concerning protocol, and to discuss the need for any protocol amendments.

6.0 PRETREATMENT EVALUATION (within 4 weeks of starting treatment):

- 6.1 History and physical examination
- 6.2 Determine IPS score. (Only patients with IPS score of 2 or higher are eligible)
- 6.3 CBC, with differential count and platelet count.
- 6.4 Serum Chemistries: glucose, BUN, creatinine, uric acid, total bilirubin, alkaline phosphatase, LDH, total protein, albumin, SGOT(AST), SGPT (ALT), and calcium.
- 6.5 Immunology: Hepatitis B and C will be tested in all patients.
- 6.6 Appropriate imaging studies which should include at least a chest x-ray (CXR), CT scans of the neck, chest, abdomen and pelvis,
- 6.7 PET scan
- 6.8 Measurement of LVEF by MUGA or echocardiogram
- 6.9 Bone marrow biopsy/aspirate
- 6.10 Serum pregnancy tests for women of child bearing age

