11. STATISTICAL CONSIDERATION
12. REPORTING REQUIREMENT
13. REFERENCES
14. APPENDIX

INFORMED CONSENT

Study Chairman: [name].

Collaborators:

~~[name]~~, M.D.

~~[name]~~, M.D.

~~[name]~~, M.D.

~~[name]~~, M.D.

~~[name]~~, M.D.

~~[name]~~, M.D.

~~[name]~~, M.D., Ph.D.

~~[name]~~, Ph.D.

1.0 OBJECTIVES:

1.1 Primary:

To evaluate the event free survival (EFS) following therapy with rituximab plus ABVD or standard ABVD in patients with newly diagnosed classical Hodgkin lymphoma who have poor prognosis defined as International prognostic score (IPS) of > 2.

1.2 Secondary:

1.2.1 To compare the effect of the two treatment arms on PET scan results after 2 cycles of therapy

1.2.2 To compare the effect of the two treatment arms on the level of circulating malignant Hodgkin stem cells

2.0 BACKGROUND:

2.1 Hodgkin lymphoma: The world health organization (WHO) classification of Hodgkin lymphoma (HL) distinguished between two major subtypes, classical HL and nodular lymphocyte predominant HL.[1] Approximately 95% of patients with HL will have the classical HL histology, which is characterized by the presence of rare malignant Hodgkin and Reed Sternberg (HRS) cells among an overwhelming number of benign reactive cells. In recent years, new studies shed more light on the biologic and molecular features of HRS cells providing hopes that new targeted therapy may be developed to enhance the cure rate and to reduce treatment-related toxicity.

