2.3 The International Prognostic Index (IPS): HL is staged according to the Cotswold modification of the Ann Arbor staging system.[12] Only imaging studies and bone marrow biopsies (clinical staging) are used for stage assignment and treatment planning. The international prognostic score (IPS) was developed to further guide therapy of patients with advanced stage HL.[11] In this model, seven factors are used [Table 1]. Using this model, 42% of patients with advanced stage HL are expected to have an IPS score of >2 (3-7), and those patients are expected to have a 55% 5-year freedom from progression with ABVD-like therapy. In contrast, patients with IPS score 0-2 are expected to have 74% 5-year freedom from progression. Thus, patients with IPS score of > 2 have a poor outcome with current standard therapy, and will be included in this proposed study.

Table 1	
International Prognostic Score (IPS) for Advanced HL[11]	
1. Sex :	male
2. Age:	≥ 45
3. Stage:	IV
4. Hemoglobin	<10.5 g/dl
5. WBC:	≥ 15,000/
6. Lymphocyte count	< 600/ or < 8% of WBC
7. Serum albumin	< 4 g/dl

2.4 Rational for using rituximab for the treatment of classical HL:

2.4.1 Role of reactive B-cells in the microenvironment: HRS cells are surrounded by an overwhelming number of reactive cellular infiltrate. These reactive cells are not bystander cells, as once thought of. In contrast, they frequently provide survival signals to HRS cells.[13] The role of the microenvironment in supporting the survival and growth of HRS cells is best illustrated by the difficulty of establishing HRS-derived cell lines. Once HRS cells are taken out of the microenvironment, it is extremely difficult to grow them in culture. It is, therefore, ironic that the host own immune cells are providing survival factors to the malignant cells, creating an “immune-betrayal” phenomenon. Therefore, we hypothesized that eliminating these reactive cells from the microenvironment may deprive HRS cells from critical survival factors and may lead to their growth arrest and death.[13]

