2.5 Results with rituximab plus ABVD: The clinical activity of rituximab in patients with relapsed classical HL (irrespective of CD20 expression by HRS cells) was recently examined by our group at M. D. Anderson Cancer Center, in which rituximab was used to deplete CD20+ reactive B lymphocytes from HL microenvironment.[15] Twenty-two heavily pretreated patients with classical HL were treated with six weekly doses of rituximab. Five (22%) patients achieved partial or complete remissions, and eight additional patients had stable disease. Clinical remissions were observed in patients irrespective of CD20 expression by HRS cells, but were observed in patients whose disease was confined to the lymph nodes. In a follow-up study, we combined rituximab with ABVD (R-ABVD) chemotherapy to treat patients with newly diagnosed classical HL.[16, 17] In this phase II study, 65 patients with classical HL were treated with R-ABVD. With a median follow up of 32 months, the estimated event-free survival (EFS) is 82% and overall survival 100%. Importantly, the EFS was improved for all risk categories: for patients with a prognostic score of 0-1 the EFS was 92%, for score 0-2 was 86%, and for score 3-5 was 73% (Fig 1, Table 2).

Table -2 : Event free survival (EFS) observed in patients treated with R-ABVD compared to historical data with ABVD alone. EFS is shown in different groups according to IPS.

IPS Group	ABVD 3-year EFS	R-ABVD 3-year EFS
0-1	79%	95%
0-2	74%	87%
2	67%	76%
>1	60%	76.5%
>2	55%	77%
>3	47%	71%

[figure not shown]

Figure 1: Event free survival (EFS) in 65 patients treated with rituximab plus ABVD (R-ABVD); (Left) results are shown in 5 risk groups according to the international prognostic score (IPS). (Right) results are shown in patients with IPS score of 0-2 and > 2. The same data is shown in Table 2.

2.6: Role of early PET imaging in predicting treatment outcome: While the IPS may predict treatment outcome in patients with advanced HL, others have recently examined

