the prognostic role of PET imaging after starting therapy. Using this approach, Hutchings and colleagues prospectively assessed the value of positron emission tomography with 2-[18F]fluoro-2-deoxy-D-glucose (FDG-PET) after two cycles of chemotherapy for prediction of progression-free survival (PFS) and overall survival (OS) in Hodgkin lymphoma (HL).[18] Seventy-seven consecutive, newly diagnosed patients underwent FDG-PET at staging, after two and four cycles of chemotherapy, and after completion of chemotherapy. After two cycles of chemotherapy, 61 patients had negative FDG-PET scans and 16 patients had positive scans. Eleven of 16 FDG-PET-positive patients progressed and 2 died. Three of 61 FDG-PET-negative patients progressed; all were alive at latest follow-up. Survival analyses showed strong associations between early FDG-PET after two cycles and PFS ($P < .001$) and OS ($P < .01$). Thus, a positive early interim FDG-PET is highly predictive of progression in patients with advanced-stage HL.

- 2.7 **Proposal:** based on the encouraging phase-II data from MDACC, we propose to confirm these results in a randomized study focusing on patients with poor risk features (IPS score > 2). Furthermore, we will compare the effect of these two treatment arms on PET imaging after 2 cycles of therapy, and on the level of circulating HL stem cells, and correlate these results with EFS.

3.0 DRUG INFORMATION:

Rituximab

Rituximab is a genetically engineered, chimeric, murine/human monoclonal antibody directed against the CD20 antigen found on the surface of normal and malignant pre-B and mature B cells. The antibody is an IgG₁ κ immunoglobulin containing murine light- and heavy-chain variable region sequences and human constant region sequences. Rituximab is composed of two heavy chains of 451 amino acids and two light chains of 213 amino acids (based on cDNA analysis) and has an approximate molecular mass of 145 kD. Rituximab has a binding affinity for the CD20 antigen of ~ 8.0 nM.

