Description: DTIC-Dome Sterile (dacarbazine) is a colorless to an ivory colored solid which is light sensitive. Each vial contains 100 mg of dacarbazine, or 200 mg of dacarbazine (the active ingredient), anhydrous citric acid and mannitol. DTIC-Dome is reconstituted and administered intravenously (pH 3-4). DTIC-Dome is an anticancer agent.

Clinical Pharmacology: In a patient with renal and hepatic dysfunction, the half-lives were lengthened to 55 minutes and 7.2 hours. Although the exact mechanism of action of DTIC-Dome is not known, three hypotheses have been offered:

1. inhibition of DNA synthesis by acting as a purine analog
2. action as an alkylating agent
3. Interaction with SH groups

Indications and Usage: DTIC-Dome is indicated in the treatment of metastatic malignant melanoma. In addition, DTIC-Dome is also indicated for Hodgkin's disease as a secondary-line therapy when used in combination with other effective agents.

Contraindications: DTIC-Dome is contraindicated in patients who have demonstrated a hypersensitivity to it in the past.

Warnings: Hemopoietic depression is the most common toxicity with DTIC-Dome and involves primarily the leukocytes and platelets, although, anemia may sometimes occur.

Leukopenia and thrombocytopenia may be severe enough to cause death. The possible bone marrow depression requires careful monitoring of white blood cells, red blood cells, and platelet levels. Hemopoietic toxicity may warrant temporary suspension or cessation of therapy with DTIC-Dome. Hepatic toxicity accompanied by hepatic vein thrombosis and hepatocellular necrosis resulting in death, has been reported. The incidence of such reactions has been low; approximately 0.01% of patients treated.

4.0 PATIENT ELIGIBILITY:

Inclusion Criteria:

- a. Previously untreated patient with classical Hodgkin's lymphoma patients with stage III and IV.
- b. International Prognostic Score of > 2 (patient must have > 2 of the following risk features: Male, ≥ 45 years of age, Stage IV, Albumin < 4 , WBC ≥ 15 , Lymphocytes $< 8\%$ or < 600 , Hgb < 10.5)
- c. Must sign a consent form
- d. Must be older than 16 years
- e. Must have adequate bone marrow reserve (ANC $\geq 1,500/uL$, Platelet $> 100,000/uL$)
- f. LVEF $\geq 50\%$ by MUGA scan or echocardiogram
- g. Serum creatinine < 2 mg/dl, serum bilirubin < 2 mg/dl, AST or ALT $< 2x$ ULN
- h. Bi-dimensionally measurable disease

Exclusion Criteria:

- a. Lymphocyte Predominant Hodgkin's Lymphoma

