According to the historical data, the three-year EFS rate is 55% for the patients treated with ABVD and 77% for the patients treated with R-ABVD. A 22% improvement in three-year EFS rate is considered a clinically significant outcome for the groups. The corresponding hazard ratio between the R-ABVD group and the ABVD group is 0.437 based on the assumption that the time to event follows an exponential distribution. Assuming two-sided type I error rate of 0.05, accrual rate of 3 patients per month, and additional 39 months of follow-up, a trial with 54 patients each arm will have 80% of power to detect a 22% improvement in three-year EFS rate. Two interim analyses will be performed to allow for the early termination of the trial in light of evidence that one treatment arm is superior to the other treatment arm or there is no difference between the two treatment arms. In order to provide an overall significance level of 0.05 for the study, the interim analyses will use a Lan-DeMets monitoring boundary with an O'Brien-Fleming stopping rule (Cytel 2004). The interim analyses will be performed when 17 and 35 out of the expected 52 events have been observed. Using O'Brien-Fleming outer test boundaries, the two-sided Z-score test cut-offs at the two interims and final analyses for rejecting the null hypothesis will be ± 3.71 , 2.51, and 1.96, respectively. The inner (futility) Z-score boundaries for stopping and accepting the null are 0.04, 0.95, and 1.96. By factoring in the 10% of patient drop-out rate, the total number of patients will be enrolled to the study is 120.

Analysis Plans

Patients' demographic information at baseline will be analyzed, with data summarized in tables listing the number of subjects per treatment group in order to assess comparability. The student t-test or the Wilcoxon test will be used to compare continuous variables between two different patient groups. The chi-square test or the Fisher's exact test will be applied to assess the association between two categorical variables. Logistic regression will be utilized to assess the effect of patient prognostic factors on the response rate.

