Expression of CD19 and CD20 will be measured overtime. The distribution of biomarkers will be examined first by the exploratory data analysis using scatter plot matrix, box plots, BLiP plot (Lee, 1997) and trellis plot, etc. Correlation among continuous biomarkers will be examined by Pearson or Spearman rank correlation coefficients. The association on discrete biomarkers will be tested by chi-square or Fisher's exact test. McNemar's test will be applied to test the change of a single discrete biomarker over time. Repeated measures analysis including mixed effects model will be performed to analyze biomarkers change over time.

Time-to-event outcomes, including event-free survival and overall survival, will be estimated using Kaplan-Meier method. The log-rank test will be performed to test the difference in time-to-event distributions between patient groups. Cox proportional hazards model will be utilized to include multiple covariates in the time-to-event analysis.

Toxicity data will be summarized by frequency tables. The association between the types and severity of toxicity and the treatment groups will be evaluated. No formal statistical testing will be performed on these summary data.

For the efficacy endpoint, intend-to-treat analysis will be applied to the randomized and eligible patients. For the toxicity endpoint, per-treated analysis will be used to include any patient who received the treatment – regardless of the eligibility nor the duration or dose of the treatment received.

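### Item 6.2 admits patients with an IPS of exactly 2, while the objective, the inclusion criterion and the sample-size rates all rest on IPS > 2

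*Combined protocol and SAP*

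**What the plan says.** Item 6.2 in Section 6.0 (Pretreatment Evaluation) tells staff to determine the IPS and adds its own eligibility rule: "Only patients with IPS score of 2 or higher are eligible".

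Every other statement of the population uses a higher threshold:

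- Section 1.1, primary objective: "poor prognosis defined as International prognostic score (IPS) of > 2".
- Section 2.3: "patients with IPS score of > 2 have a poor outcome with current standard therapy, and will be included in this proposed study". The same paragraph glosses > 2 as scores 3 to 7 and puts a score of 2 in the better-risk comparison group, 0-2.
- Section 2.7: "randomized study focusing on patients with poor risk features (IPS score > 2".
- Section 4.0, inclusion b: "International Prognostic Score of > 2 (patient must have > 2 of the following risk features".

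Section 11.0 (Sample Size and Power) names no IPS group but states that "the three-year EFS rate is 55% for the patients treated with ABVD and 77% for the patients treated with R-ABVD". Section 11.0 (Analysis Plans) limits the efficacy analysis: "intend-to-treat analysis will be applied to the randomized and eligible patients".

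**The concern.** IPS > 2 is what makes this a poor-risk trial. Item 6.2 and inclusion b disagree about a patient with exactly two risk factors, and item 6.2 sits at the point where the score is worked out. In a multi-centre trial, sites could apply different thresholds in good faith.

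Two things are at stake. First, because efficacy is analysed in patients who are both randomized and eligible, someone with IPS 2 enrolled under item 6.2 could be kept by citing that item or dropped by citing inclusion b. That dispute would arise after randomization, possibly with outcomes known. Second, either choice can cost power: keeping such patients may dilute the effect, and dropping them loses events.

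**Working it through.** **Which population the design uses.** Table 2 (Section 2.5) gives three-year EFS by IPS group. The hazard ratio (HR) under exponential survival is ln(R-ABVD rate)/ln(ABVD rate).

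| IPS group | ABVD | R-ABVD | HR |
|---|---|---|---|
| > 2 (inclusion b) | 55% | 77% | ln 0.77/ln 0.55 = 0.437 |
| > 1 (item 6.2) | 60% | 76.5% | ln 0.765/ln 0.60 = 0.524 |
| 2 (patients item 6.2 adds) | 67% | 76% | ln 0.76/ln 0.67 = 0.685 |

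Section 11.0 uses 55%, 77% and 0.437. Only the > 2 row fits.

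**Reproducing the plan.** With two-sided alpha 0.05, 80% power and 1:1 allocation, Freedman's formula gives (1.960 + 0.842)² × [(1 + 0.437)/(1 − 0.437)]² = 51.2, so 52 events, as stated. Schoenfeld's formula gives 46. Accrual of 3 per month plus 39 months of follow-up yields 50.9 expected events from 108 patients, close to 52. Then 108/0.9 = 120. The plan's figures hold together for IPS > 2.

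**If patients with IPS 2 are enrolled and analysed.** Let p be their share. The ABVD rate is 0.55(1 − p) + 0.67p and the R-ABVD rate is 0.77(1 − p) + 0.76p. Freedman power is Φ(√52 × (1 − HR)/(1 + HR) − 1.96); Schoenfeld power is Φ(√52 × |ln HR|/2 − 1.96).

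| p | ABVD | R-ABVD | HR | Freedman | Schoenfeld |
|---|---|---|---|---|---|
| 0 | 55.0% | 77.0% | 0.437 | 81% | 85% |
| 10% | 56.2% | 76.9% | 0.456 | 77% | 81% |
| 20% | 57.4% | 76.8% | 0.476 | 73% | 76% |
| 30% | 58.6% | 76.7% | 0.496 | 68% | 71% |

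Freedman is the better guide here because it reproduces the plan's 52 events. A simulated group-sequential log-rank test used the plan's boundaries, with the final look at 52 events or 39 months after last entry and 6,000 trials per cell. It gave 81, 76, 71 and 66% with 108 patients, and 82, 77, 73 and 68% with 120.

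**If entry at IPS 2 or higher were unrestricted.** The share p can be backed out of the document in three ways:

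- ABVD column: (60 − 55)/(67 − 55) = 42%.
- R-ABVD column: (77 − 76.5)/(77 − 76) = 50%.
- Rows 0-1, 0-2 and 2, with Section 2.3's 42% for > 2: (79 − 74)/(79 − 67) × 0.58 = 0.242, and 0.242/(0.242 + 0.42) = 37%.

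Freedman power is then 64% (p = 37%), 62% (42%) or 57% (50%). The simulation gives 58% and 54% with 108 patients, and 62% and 57% with 120, for 42% and 50%. Using the > 1 row directly (HR 0.524), power at 52 events is 61% (Freedman) or 64% (Schoenfeld).

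**If the effect does not depend on IPS.** With HR 0.437 assumed at IPS 2 as well, power at 52 events stays about 80%. In the simulation, where the final look may come before 52 events, it is 76-80% with 108 patients and 79-82% with 120.

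**If patients with IPS 2 are enrolled and then excluded.** With 120 enrolled and no drop-out, 57.8 events are expected. Excluding 10% leaves 57.8 × 0.9 = 52.0 events and 81% Freedman power. Excluding 20% leaves 57.8 × 0.8 = 46.3 events and 76%. The first case already uses up the plan's drop-out allowance.

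**The case against.** The strongest reply is that item 6.2 is a slip. It is a parenthetical in a list of tests, while Section 4.0 is the eligibility section and lists the factors. Sections 2.3 and 2.7 describe the intended population less strictly than 1.1 and 4.0. Nothing shows that any site followed item 6.2. Sections 5.1 and 5.2 are not in the available text, so a check at registration cannot be ruled out, and Section 5.10 provides quarterly calls to review enrollment. It may well be a slip. But it is a slip in an eligibility rule, on the variable that defines the population, and no available passage gives Section 4.0 precedence.

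The objection to the power figures largely stands as a caution on size:

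- The R-ABVD rates come from subgroups of one 65-patient phase II study, and the better-risk IPS 2 group does slightly worse (76%) than IPS > 2 (77%). Most of the modelled dilution comes from taking that at face value.
- The 50% share divides half a point by one point. Rounding alone could put it anywhere, so the 57% figure deserves little weight.
- The text of Section 2.5 reports "for score 0-2 was 86%, and for score 3-5 was 73"%, against 77% for > 2 in Table 2. A 73% versus 55% comparison has HR 0.526 and 61% power at 52 events even without any IPS 2 patients.
- Section 2.3 presents the 55% as a 5-year figure.
- Under inclusion b, patients with IPS 2 would be excluded, so lost events may be likelier than dilution.

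None of this affects the contradiction, which does not depend on any power calculation.

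**Conclusion.** The concern holds and must be fixed. Item 6.2 states a different eligibility threshold from the objective and inclusion b, and the design figures belong to IPS > 2. Confidence in the contradiction is high.

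Confidence in the size of any power loss is low. It requires that sites follow item 6.2, that the patients so enrolled are analysed, and that the Table 2 rates are right. On those assumptions, power falls from about 81% to 68-77% with 10-30% IPS 2 patients, and to roughly 57-64% under unrestricted entry. If the treatment effect is the same at IPS 2, there is little or no loss.

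**What to change.** Align item 6.2 with inclusion b so that it reads: Only patients with IPS score of > 2 (3 or higher) are eligible. Send a notice to all sites. The hazard ratio of 0.437, 52 events, 54 patients per arm and total of 120 all stand.

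The cost is a one-line amendment and the notice. Accrual may slow if any site has been using item 6.2. How to analyse any patient with IPS 2 already randomized is a separate question that this correction does not settle.

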7.0 EVALUATION DURING THE CHEMOTHERAPY ADMINISTRATION

- 7.1 CBC with differential at the beginning of each ABVD dose (within 2 days)
- 7.2 Monthly serum electrolytes
- 7.3 Repeat imaging studies every 2 cycles of ABVD.
- 7.4 PET scan after 2 cycles of therapy (approximately 2 months), and every 2 cycles until it becomes negative (if clinically indicated) .
- 7.5 Repeat bone marrow biopsy/aspirate if was positive prior to starting therapy at the end of ABVD therapy.

8.0 FOLLOW UP EVALUATION

After completion of therapy, patients will have follow up evaluation to determine the disease status every 3 months during the first year of follow up, every 4 months during the second year, every 6 months during years 3-5, and once a year thereafter. Follow up evaluation will include physical examination and appropriate blood tests and imaging studies, as clinically indicated.

9.0 CRITERIA FOR RESPONSE:

The Revised Response Criteria for Malignant Lymphoma^[19] will be used as shown in Table-3 :

Response Definitions for Clinical Trials

Response	Definition	Nodal Masses	Spleen, Liver	Bone Marrow
CR	Disappearance of all evidence of disease	(a) FDG-avid or PET positive prior to therapy; mass of any size permitted if PET negative (b) Variably FDG-avid or PET negative; regression to normal size on CT	Not palpable, nodules disappeared	Infiltrate cleared on repeat biopsy; if indeterminate by morphology, immunohistochemistry should be negative
PR	Regression of measurable disease and no new sites	\geq 50% decrease in SPD of up to 6 largest dominant masses; no increase in size of other nodes (a) FDG-avid or PET positive prior to therapy; one or more PET positive at previously involved site (b) Variably FDG-avid or PET negative; regression on CT	\geq 50% decrease in SPD of nodules (for single nodule in greatest transverse diameter); no increase in size of liver or spleen	Irrelevant if positive prior to therapy; cell type should be specified
SD	Failure to attain CR/PR or PD	(a) FDG-avid or PET positive prior to therapy; PET positive at prior sites of disease and no new sites on CT or PET (b) Variably FDG-avid or PET negative; no change in size of previous lesions on CT		
Relapsed disease or PD	Any new lesion or increase by \geq 50% of previously involved sites from nadir	Appearance of a new lesion(s) $>$ 1.5 cm in any axis, \geq 50% increase in SPD of more than one node, or \geq 50% increase in longest diameter of a previously identified node $>$ 1 cm in short axis Lesions PET positive if FDG-avid lymphoma or PET positive prior to therapy	$>$ 50% increase from nadir in the SPD of any previous lesions	New or recurrent involvement

Abbreviations: CR, complete remission; FDG, [¹⁸F]fluorodeoxyglucose; PET, positron emission tomography; CT, computed tomography; PR, partial remission; SPD, sum of the product of the diameters; SD, stable disease; PD, progressive disease.

10.0 CRITERIA FOR DISCONTINUING THERAPY:

- Active HBV infection or hepatitis (Subjects who are carriers of hepatitis B at the time of discontinuation from study treatment will continue to be followed for clinical and laboratory signs of active HBV infection and for signs of hepatitis)
- Severe or life-threatening anaphylaxis or hypersensitivity reaction
- Inability of subject to comply with study requirements
- Determination by the investigator that it is no longer safe for the subject to continue therapy
- Increasing disease, at any time during treatment or of less than PR after a minimum of 6 courses of therapy. Sometimes, a patient's disease will

progress so rapidly that it is appropriate to change therapy after a single course. Patients who are not responding will be considered failures on this regimen and if medically stable will be offered an alternative regimen. Patients who develop unacceptable toxicity should be removed from the study.

- Grade 3 or 4 non-hematologic toxicity that are not predicted by ABVD or R-ABVD (alopecia, nausea/vomiting, neuropathy).
- Patient's refusal to continue therapy.

11.0 STATISTICAL CONSIDERATION:

This is a trial to study the chemotherapy ABVD (Adriamycin, Bleomycin, Vinblastine, and Dacarbazine) with or without rituximab in treating patients with Hodgkin Lymphoma. Patients will be enrolled into the study at the accrual rate of 3 patients per month with an additional thirty-nine months follow-up period.

Objective

The primary objective of the study is to evaluate the efficacy of the combination regimen of rituximab and ABVD chemotherapy (R-ABVD) and ABVD alone measured as event-free survival (EFS).

Sample Size and Power

According to the historical data, the three-year EFS rate is 55% for the patients treated with ABVD and 77% for the patients treated with R-ABVD. A 22% improvement in three-year EFS rate is considered a clinically significant outcome for the groups. The corresponding hazard ratio between the R-ABVD group and the ABVD group is 0.437 based on the assumption that the time to event follows an exponential distribution. Assuming two-sided type I error rate of 0.05, accrual rate of 3 patients per month, and additional 39 months of follow-up, a trial with 54 patients each arm will have 80% of power to detect a 22% improvement in three-year EFS rate. Two interim analyses will be performed to allow for the early termination of the trial in light of evidence that one treatment arm is superior to the other treatment arm or there is no difference between the two treatment arms. In order to provide an overall significance level of 0.05 for the study, the interim analyses will use a Lan-DeMets monitoring boundary with an O'Brien-Fleming stopping rule (Cytel 2004). The interim analyses will be performed when 17 and 35 out of the expected 52 events have been observed. Using O'Brien-Fleming outer test boundaries, the two-sided Z-score test cut-offs at the two interims and final analyses for rejecting the null hypothesis will be ± 3.71 , 2.51, and 1.96, respectively. The inner (futility) Z-score boundaries for stopping and accepting the null are 0.04, 0.95, and 1.96. By factoring in the 10% of patient drop-out rate, the total number of patients will be enrolled to the study is 120.

Analysis Plans

Patients' demographic information at baseline will be analyzed, with data summarized in tables listing the number of subjects per treatment group in order to assess comparability. The student t-test or the Wilcoxon test will be used to compare continuous variables between two different patient groups. The chi-square test or the Fisher's exact test will be applied to assess the association between two categorical variables. Logistic regression will be utilized to assess the effect of patient prognostic factors on the response rate.

Expression of CD19 and CD20 will be measured overtime. The distribution of biomarkers will be examined first by the exploratory data analysis using scatter plot matrix, box plots, BLiP plot (Lee, 1997) and trellis plot, etc. Correlation among continuous biomarkers will be examined by Pearson or Spearman rank correlation coefficients. The association on discrete biomarkers will be tested by chi-square or Fisher's exact test. McNemar's test will be applied to test the change of a single discrete biomarker over time. Repeated measures analysis including mixed effects model will be performed to analyze biomarkers change over time.

Time-to-event outcomes, including event-free survival and overall survival, will be estimated using Kaplan-Meier method. The log-rank test will be performed to test the difference in time-to-event distributions between patient groups. Cox proportional hazards model will be utilized to include multiple covariates in the time-to-event analysis.

Toxicity data will be summarized by frequency tables. The association between the types and severity of toxicity and the treatment groups will be evaluated. No formal statistical testing will be performed on these summary data.

For the efficacy endpoint, intend-to-treat analysis will be applied to the randomized and eligible patients. For the toxicity endpoint, per-treated analysis will be used to include any patient who received the treatment – regardless of the eligibility nor the duration or dose of the treatment received.

